5.2 Exclusion Criteria

Participants are excluded from the study if any of the following criteria apply:

Medical Conditions

1. Acute (time-limited) or febrile (temperature $\geq 38.0^{\circ}\text{C}$ [100.4°F]) illness/infection within 3 days of planned dosing; participants excluded for transient acute illness may be dosed if illness resolves.
2. History of a clinically significant bleeding disorder (eg, factor deficiency, coagulopathy, or platelet disorder), or prior history of significant bleeding or bruising following IM injections or venipuncture.
3. History of hypersensitivity to any component of the study vaccination.
4. History of severe adverse reaction associated with a vaccine and/or severe allergic reaction (eg, anaphylaxis).
5. Known or suspected congenital or acquired immunodeficiency.
6. Known or suspected autoimmune condition as determined by history and/or physical examination.
7. History of Guillain-Barré syndrome or any other demyelinating condition.
8. History of malignancy other than treated non-melanoma skin cancers or locally-treated cervical cancer in previous 5 years.
9. Any condition that may significantly increase the risk to the participant because of participation in the study, impact the participant's ability to participate in the study, or impair the interpretation of the study data.

Prior/Concomitant Therapy

10. Receipt of any licensed or investigational RSV and/or hMPV vaccine any time prior to administration of study intervention.
11. Receipt of any licensed vaccine (other than licensed influenza or COVID-19 vaccines) within 28 days prior to or expected receipt within 28 days after administration of study intervention. Licensed influenza or COVID-19 vaccines are permitted beginning >14 days prior to and >14 days after administration of study intervention
12. Receipt of immunoglobulin or blood products within 3 months prior to administration of study intervention or expected receipt during the study.
13. Receipt of immune-modifying drugs or immunosuppressive therapy, such as anti-cancer chemotherapy or radiation therapy within 6 months prior to enrollment (or expected receipt during study), or long-term systemic corticosteroid therapy (prednisolone or equivalent at a dose of ≥ 20 mg daily or every other day for more than 2 consecutive weeks) within 6 months prior to study intervention or anticipated receipt during study. Topical/inhaled steroids or short-term oral steroids are permitted.

Prior/Concurrent Clinical Study Experience

14. Participation in another study or receiving interventional study investigational medicinal product (IMP), in the preceding 28 days or expected receipt of another study intervention (or participation in another study) during the period of study follow-up.

Other Exclusions

15. Employees of the Sponsor involved in planning, executing, supervising, or reviewing the IVX-A12 program, clinical study site staff, or any other individuals involved with the conduct of the study, or immediate family members of such individuals.
16. Alcohol or substance abuse that, in the opinion of the Investigator, might interfere with the study conduct or completion.
17. Deprived of freedom by an administrative or court order, or in emergency setting, or hospitalized involuntarily.
18. Judgment by the Investigator that the participant should not participate in the study if the participant is unlikely to comply with study procedures, restrictions, and requirements.

5.3 Lifestyle Considerations

Restrictions relating to concomitant medications are described in [Section 6.9](#).

5.4 Screen Failures

A screen failure occurs when a participant who has consented to participate in the clinical study is not subsequently assigned to study intervention. A minimal set of screen failure information is required to ensure transparent reporting of screen failure participants to meet the Consolidated Standards of Reporting Trials (CONSORT) publishing requirements and to

respond to queries from regulatory authorities. Minimal information includes demography, screen failure details, eligibility criteria, and any SAE.

Individuals who do not meet the criteria for participation in this study (screen failure) may be rescreened. Only a single rescreening is allowed in the study. Rescreened participants should be assigned the same participant number as for the initial screening.

5.5 Criteria for Temporarily Delaying Enrollment, Randomization, or Administration of Study Intervention

The clinical trial enrollment will be halted if there is clear evidence of potential harm or harmful effects. Vaccine administration will be paused for further review and assessment if any of the following events occur:

- Any SAE (including death and serious allergic or hypersensitivity reaction) or AESI (see Section 8.4.7) that could be related to vaccine as per the Investigator or Sponsor.
- ≥ 3 participants per group experiencing \geq Grade 3 unsolicited non-serious reaction of the same or similar type (not explained by any other possible etiology) assessed as related to study vaccine.

If any of the above criteria are met, a decision will be made as to whether dosing in the study will be allowed to resume.

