6.4 Blinding

Neither the participant nor any of the Investigators or Sponsor staff who are involved in the treatment or clinical evaluation and monitoring of the participants will be aware of the study intervention received. Since IVX-A12 and AREXVY are visually distinct prior to dose preparation (due to differences in packaging), the study intervention will be handled by an unblinded pharmacist and may be administered by an unblinded administrator (or designee, in accordance with local and institutional regulations) at the study site who will be independent of safety evaluations and other trial evaluations if another blinded study site member trained to give IMP injections is not available. Thus, personnel preparing and administering study intervention may be the same individual. Syringe masking will be required in order to maintain the blind. Refer to the Pharmacy Manual for detailed information on syringe masking procedures for IVX-A12 and AREXVY.

The following personnel will have access to the randomization list during the study, prior to clinical database lock:

- Those generating the randomization list and IRT/RTSM system

The randomization code should not be broken except in medical emergencies when the appropriate management of the participant requires knowledge of the treatment randomization. The Investigator documents and reports the action to the Sponsor, without revealing the treatment given to participant to the Sponsor staff.

The Sponsor retains the right to break the code for SAEs that are unexpected and are suspected to be causally related to an IMP and that potentially require expedited reporting to regulatory authorities. Randomization codes will not be broken for the planned analyses of data until all decisions on the evaluability of the data from each individual participant have been made and documented.

The IRT/RTSM will be programmed with blind-breaking instructions. Unblinding should only occur within the IRT/RTSM system. In case of an emergency, in which the knowledge of the specific blinded study intervention will affect the immediate management of the participant's condition, the Investigator has the sole responsibility for determining if unblinding of a participants' intervention assignment is warranted. Participant safety must always be the first

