7.1 Discontinuation of Study Intervention

Each participant will receive one dose of study intervention. An individual participant will not receive study intervention if any of the following occur in the participant in question:

- Participant withdraws consent after signing the ICF
- Participant meets any of the exclusion criteria or fails to meet all inclusion criteria for study participation (see [Section 5.1](#) and [5.2](#))

Each participant who has received study intervention will be followed for the full study period unless consent is withdrawn specifically from further study participation, or the participant is lost to follow-up.

Note that discontinuation from study intervention is *not* the same thing as a discontinuation or withdrawal from the study (see [Section 7.2](#)).

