9.6 Data Monitoring Committee

Not applicable.

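### The second dosing-pause criterion in Protocol 5.5 counts cases per group, so staff blinded under 6.4 cannot tell at 3 or 4 pooled cases whether it is met

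*Protocol*

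**What the plan says.** Protocol 5.5 states that "Vaccine administration will be paused for further review and assessment" if either of two criteria is met. The first is "Any SAE (including death and serious allergic or hypersensitivity reaction) or AESI" that could be related to vaccine. The second applies at 3 or more participants in a group with a non-serious, unsolicited reaction of Grade 3 or higher, of the same or similar type, without another explanation and judged related. Its wording is "3 participants per group experiencing". Section 5.5 does not say who makes the count or who decides whether dosing resumes.

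On blinding, Protocol 6.4 says: "Neither the participant nor any of the Investigators or Sponsor staff who are involved in the treatment or clinical evaluation and monitoring" of participants will know the assignment. Before database lock, list access is given only to "Those generating the randomization list and IRT/RTSM system". The code may be broken in a medical emergency. In addition, "The Sponsor retains the right to break the code for SAEs that are unexpected" and suspected to be related. The unblinded pharmacist and administrator are kept independent of safety evaluation.

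The section headed "9.6 Data Monitoring Committee" reads not applicable. Appendix A 5 leaves safety monitoring to sponsor representatives in consultation with Patient Safety and mentions no by-group data. Section 7.1 says "Each participant will receive one dose of study intervention", and 9.5 places the primary analysis after all participants have completed Day 29.

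**The concern.** The criterion is mandatory and needs a count by vaccine group. The people who would apply it are blinded, and the events it covers are non-serious by definition, so the sponsor's right to break the code for SAEs does not reach them. The first planned by-group analysis comes after all dosing has ended, when nothing is left to pause.

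The trigger exists to protect participants. At the counts where it should first act, staff who follow the text have no stated means of knowing whether a pause is required. Section 5.5 and Section 6.4 therefore conflict; the problem is more than missing operational detail.

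**Working it through.** The documents give no operating characteristics for the pause rule, so there is no figure to reproduce.

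**Inputs**
- Threshold: 3 in a group (Protocol 5.5).
- Group sizes: about 70 and 70 (Protocol 4.1).
- Grade 3 or higher is read as severe on the Appendix B 2 scale, because Tables 6 and 7 grade solicited reactions only.
- Event rate: not documented. Assumed 0.5% and 1% per participant for one single reaction type, equal in both groups. As a rough guide to scale, Protocol 2.3.1 reports over 300 older adults with no vaccine-related medically attended events to Day 28. For 0 of 300 the one-sided 95% upper limit is 1 − 0.05^(1/300) = 1.0%. This is an imperfect proxy: a severe reaction need not be medically attended, and it says nothing about AREXVY.
- Accrual: not documented. Assumed 70 of 140 (35 per group) dosed and observed while dosing continues.

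**Step 1: which pooled counts settle the criterion.**

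| Pooled cases | Splits that meet it | Splits that do not | Decidable under the blind? |
|---|---|---|---|
| 2 or fewer | none | all | yes, not met |
| 3 | 3+0 | 2+1 | no |
| 4 | 4+0, 3+1 | 2+2 | no |
| 5 or more | all | none | yes, met |

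**Step 2: chance of being met, given the pooled count.** With cases split at random between 70 and 70:
- 3 cases: 2 × C(70,3) / C(140,3) = 109,480 / 447,580 = 24.5%.
- 4 cases: 1 − C(70,2)² / C(140,4) = 1 − 5,832,225 / 15,329,615 = 62.0%.

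A fair-coin split gives 25% and 62.5%. If one group carries 80% of the cases, the figures are 52% and 85%, so the pooled count still does not settle it.

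**Step 3: how often this arises.** Let X1 and X2 be independent Binomial(35, p), with no earlier pause.

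| Assumed p, one reaction type | 0.5% | 1% |
|---|---|---|
| P(X1+X2 ≥ 3), pooled rule | 0.53% | 3.3% |
| P(max(X1,X2) ≥ 3), per-group rule | 0.145% | 1.03% |
| Difference (percentage points) | 0.4 | 2.3 |
| P(per-group rule met with 3 or 4 pooled) | 0.14% | 0.96% |

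Check of the last row at 1%: P(3 pooled) = 0.02792 and P(4 pooled) = 0.00472. With 35 per group, the chances of meeting the criterion are 0.2391 and 0.6139. So 0.02792 × 0.2391 + 0.00472 × 0.6139 = 0.0096.

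Of the trials in which the per-group rule is met, 98% (at 0.5%) and 93% (at 1%) meet it at 3 or 4 pooled cases.

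**Step 4: same or similar type.** The rates above belong to one reaction type. If 1% is instead the rate for the whole class, spread equally over independent types, the 0.96% falls to 0.28% with two types and 0.08% with four. The number of types is an assumption.

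**The case against.** The strongest reply has four parts.

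- **A count is feasible.** The criterion needs one yes-or-no answer: has either group reached 3? Someone who holds the list could give it without any evaluator learning an assignment, and 6.4 does not blind every member of sponsor staff. This stands. It shows that the gap can be closed, but neither 5.5 nor 6.4 assigns the task.
- **Another plan may assign it.** SAP section 1 refers to a Study Integrity Plan and Appendix A 7 to a Monitoring Plan; neither was supplied. This also stands. A reader might infer that no by-group safety review exists, or that a required pause would be missed. The documents do not support either inference: they show only that the protocol is silent on routing. If another plan does name an unblinded reviewer, the access list in 6.4 is incomplete and should include that role.
- **The more worrying reactions are caught elsewhere.** Under Appendix B 2, medically important events should usually be classed as serious, and Table 6 sends necrosis and exfoliative dermatitis to SAE reporting. One possibly related SAE or AESI pauses dosing with no group count. The separate halt for evidence of harm also needs no group data. This stands and narrows the point to severe, related reactions judged not medically important.
- **Staff may pause at 3 pooled cases anyway.** Nothing forbids it, but 5.5 does not require it. If that is the intended practice, the text should say so.

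**Conclusion.** The point holds as a narrow conflict within the protocol. As written, the second pause criterion cannot be decided by blinded staff at 3 or 4 pooled cases. That result is exact and does not depend on any assumed rate.

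The exposure does depend on assumptions, and it is small: 0.14% to 0.96% of trials at 0.5% to 1% for a single reaction type, equal rates and 35 per group observed, and less if that rate covers several types. A larger exposure could be obtained from higher rates or by counting all 140 participants. Neither is a sound basis here: higher rates exceed the 1.0% limit from the only, imperfect, proxy in the documents, and once all 140 are dosed there is no dosing left to pause.

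Confidence is high that the protocol text does not let the trigger be applied at those counts. It is not high that a pause would actually be missed, because the unsupplied plans may route the count. This is a cheap improvement to a participant-protection rule.

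**What to change.** Restate the second criterion in 5.5 as 3 or more participants pooled across both groups, leading to a pause for review. Blinded staff can apply this, and it never misses a per-group trigger, because 3 in one group means at least 3 pooled.

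The cost is one sentence, made through a protocol amendment that needs IRB/IEC and applicable regulatory approval (Appendix A 1), and no extra participants, visits or procedures. The pooled rule is more sensitive. It pauses for review in about 0.4 to 2.3 percentage points more trials at the assumed rates, roughly 3 to 4 times as often as the per-group rule (3.3/1.03 and 0.53/0.145), including after a 2+1 split.

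If the sponsor prefers to keep the per-group threshold, name in 5.5, and add to the 6.4 access list, a firewalled role that tells the blinded team only whether either group has reached 3. This adds no pauses beyond those the present rule intends.

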6 STUDY INTERVENTION(S) AND CONCOMITANT THERAPY

Study interventions are all pre-specified, IMPs and non-investigational medicinal product (NIMPs), medical devices and other interventions (eg, surgical and behavioral) intended to be administered to the study participants during the study conduct.

6.1 Study Intervention(s) Administered

Participants will be randomized in a 1:1 ratio to receive either IVX-A12 or AREXVY on Visit 1. Details of these study interventions are presented in Table 3.

It is recommended that the study interventions be administered as an IM injection into the deltoid of the non-dominant arm.

All study participants will be observed in the clinic for at least 30 minutes after administration of study intervention (see [Section 8.3.5.1](#)). Allergic reactions to vaccines are possible. Therefore, appropriate drugs and medical equipment to treat acute anaphylactic reactions must be immediately available, and study personnel must be trained to recognize and treat anaphylaxis.

Table 3 **Study Interventions**

Intervention name	IVX-A12	AREXVY
Type	Vaccine	Vaccine
Dose formulation	0.6 mg/mL IVX-121 and 0.6 mg/mL of IVX-241 in aqueous buffer (20 mM Tris, 100 mM NaCl, 4% (w/v) Trehalose, 0.05% (v/v) PS-20, pH 7.4).	Solid concentrate for suspension for injection supplied as a single-dose vial of lyophilized antigen component to be reconstituted with the accompanying vial of adjuvant suspension component
Unit dose strength(s)	0.5 mL	0.5 mL
Dosage level(s)	Single IM dose of 300 µg (150 µg RSV / 150 µg hMPV)	Single IM dose of 120 µg RSVPreF3 antigen
Route of administration	IM injection	IM injection
Use	Investigational	Active Comparator
IMP or NIMP/AxMP	IMP	IMP
Sourcing	Icosavax	Icosavax
Packaging and labelling	Study intervention will be provided in a glass vial. Each glass vial will be labelled as required per country requirement.	AREXVY will be packaged and labelled as required per country requirement.

6.2 Preparation, Handling, Storage, and Accountability

- The Investigator or designee (eg, unblinded pharmacist) must confirm appropriate conditions (eg, temperature) have been maintained during transit for all study intervention received at the site and throughout the entire study until authorization is provided for on-site destruction or removal of the IMP, reflecting completion of the study. In the event of a temperature excursion detected at any time during the study, sites will follow the reporting procedures for notifying the Sponsor (or designated party); release of IMP for clinical use can only occur once the event has been reviewed and approval is provided by the Sponsor (or designated party).
- Only participants enrolled in the study may receive study intervention, and only authorized site staff may supply, prepare, or administer study intervention. All study intervention must be stored in a secure, environmentally-controlled, and monitored (manual or automated) area in accordance with the labelled storage conditions with access limited to the Investigator and authorized site staff.

- The Investigator, institution, and the head of the medical institution (where applicable) is responsible for study intervention accountability, reconciliation, and record maintenance (ie, receipt, reconciliation, and final disposition records).
- Further guidance and information for the final disposition of unused study interventions are provided in the Pharmacy Manual or specific handling instructions.

6.2.1 Dose Preparation

The dose of IVX-A12 and AREXVY for administration must be prepared by the unblinded pharmacy staff members (or an appropriate designee trained in study drug preparation), using aseptic technique in compliance with local regulations and site requirements.

Doses of AREXVY vaccine administered as part of this study will be prepared in accordance with current local pharmacy or clinic guidelines per the USPI.

Refer to the Pharmacy Manual for detailed information on dose preparation and handling procedures for IVX-A12 and AREXVY.

6.2.2 Dose Administration

IVX-A12 must reach room temperature prior to administration. Once the IVX-A12 vial is punctured to perform dilution and drawn into a syringe for administration, the dose must be administered within 4 hours of vial puncture. The study intervention will be administered as a single IM injection, according to standard procedures for IM injections.

Doses of AREXVY vaccine administered as part of this study will be administered in accordance with current local pharmacy or clinic guidelines per the USPI.

The dose of IVX-A12 and AREXVY may be administered by an unblinded pharmacy staff member (or an appropriate designee in accordance with local and institutional regulations) who is independent of safety and other trial evaluations.

Once the IMP administration is completed, the syringe must be discarded with the blinding cover in place to ensure that the blind is maintained.

Refer to the Pharmacy Manual for detailed information on dose administration for IVX-A12 and AREXVY.

6.3 Assignment to Study Intervention

All participants will be centrally assigned to randomized study intervention using an Interactive Response Technology (IRT)/ Randomization and Trial Supply Management (RTSM). Randomization will be centrally stratified by age (60 to 69, 70 to 79, and \geq 80 years

of age). Before the study is initiated, the telephone number and call-in directions for the IRT and/or the log in information and directions for the RTSM will be provided to each site.

Study intervention will be dispensed at the study visits summarized in the SoA ([Section 1.3](#)). Returned study intervention should not be re-dispensed to the participants.

The IRT/RTSM will provide to the Investigator(s) or pharmacists the kit identification number to be allocated to the participant at the dispensing visit. Routines for this will be described in the IRT/RTSM user manual that will be provided to each center.

6.4 Blinding

Neither the participant nor any of the Investigators or Sponsor staff who are involved in the treatment or clinical evaluation and monitoring of the participants will be aware of the study intervention received. Since IVX-A12 and AREXVY are visually distinct prior to dose preparation (due to differences in packaging), the study intervention will be handled by an unblinded pharmacist and may be administered by an unblinded administrator (or designee, in accordance with local and institutional regulations) at the study site who will be independent of safety evaluations and other trial evaluations if another blinded study site member trained to give IMP injections is not available. Thus, personnel preparing and administering study intervention may be the same individual. Syringe masking will be required in order to maintain the blind. Refer to the Pharmacy Manual for detailed information on syringe masking procedures for IVX-A12 and AREXVY.

The following personnel will have access to the randomization list during the study, prior to clinical database lock:

- Those generating the randomization list and IRT/RTSM system

The randomization code should not be broken except in medical emergencies when the appropriate management of the participant requires knowledge of the treatment randomization. The Investigator documents and reports the action to the Sponsor, without revealing the treatment given to participant to the Sponsor staff.

The Sponsor retains the right to break the code for SAEs that are unexpected and are suspected to be causally related to an IMP and that potentially require expedited reporting to regulatory authorities. Randomization codes will not be broken for the planned analyses of data until all decisions on the evaluability of the data from each individual participant have been made and documented.

The IRT/RTSM will be programmed with blind-breaking instructions. Unblinding should only occur within the IRT/RTSM system. In case of an emergency, in which the knowledge of the specific blinded study intervention will affect the immediate management of the participant's condition, the Investigator has the sole responsibility for determining if unblinding of a participants' intervention assignment is warranted. Participant safety must always be the first

consideration in making such a determination. If a participant's intervention assignment is unblinded, the Sponsor must be notified within 24 hours after breaking the blind. The Investigator documents and reports the action to the Sponsor, without revealing the treatment given to participant to the Sponsor staff.

